The clinical study presented here will show that using a $CO_2 9.3 \mu m$ short pulsed laser irradiation markedly inhibits caries progression in pits and fissures in comparison to fluoride varnish alone over 12 months.

Study Design

[x]Randomized []Investigational intervention without random assignment

[x]Blinded, Single, []Blinded, Double

[x]Prospective [x]Control []Behavioral

Study's formal designation:

[]Phase I [x]Phase II []Phase III []Phase IV

Framework:

[x] superiority [] equivalence [] non inferiority [] exploratory

Study type

The CHR application will be a minimal risk, full committee review application.

Methodology

Specific Aims

A) The aim of the study is to assess if the use of the new CO₂ - 9.3µm short-pulsed laser in addition to fluoride therapy allows rendering occlusal pit and fissures caries resistant in comparison to fluoride therapy alone in participants in a randomized, single blind, prospective, split mouth controlled, clinical trial. The fissure mineral loss will be quantified by visual exams with the International Caries Detection and Assessment System (ICDAS II), SOPROLIFE daylight and blue fluorescence, and by DIAGNOdent Laser Light-induced Fluorescence.

Primary study outcome measures

Differences in change in ICDAS scores between matched case and control teeth (within patient) from baseline to 6 months and baseline to 12 months

Differences in occurrence of ICDAS 3 scores between matched case and control teeth (within patient) from baseline to 6 months and baseline to 12 months

Secondary study outcome measures

Differences in change in SOPROlife scores between matched case and control teeth (within patient) from baseline to 6 months and baseline to 12 month

Material & Methods

Clinical Study:

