The primary analysis of this study will compare ICDAS scores for the laser group vs. controls. To this end, we will perform mixed effects proportional odds regression modeling with outcomes of ICDAS and SOPROLIFE scores. These models will explicitly account for within patient clustering and will include group (laser vs. control) as the main predictor along with tooth site and additional potential moderating variables such as age, sex, snack habit measures, tooth brushing habit, and dental history predictors. Importantly, we will include interactions of these additional predictors with the group predictor as well as time, which may indicate whether there is possible differential protectiveness of laser (over time) in specific subgroups. The models will be explored in a bottom up approach with each predictor considered in models one at a time along with group, group by predictor interaction and tooth site. If we see important effects, we will then combine a small number of predictors based on scientific plausibility in a single model, though we note that these will be far from definitive models given the sample size and scope of the proposed study. P \leq 0.05 will be considered statistically significant though we will emphasize that any model results are highly speculative and will require independent verification.

IRB approval

Investigational Review Board approval (UCSF Committee on Human Research CHR) will be achieved before the study will be started.

If requested the IRB can additionally scrutinize the study and will state that the study was conducted under the rules of GCP - Good Clinical Practice.

References

- [1] Chan, A. W., Tetzlaff, J. M., Altman, D. G., Laupacis, A., Gotzsche, P. C., Krleza-Jeric, K., Hrobjartsson, A., Mann, H., Dickersin, K., Berlin, J. A., Dore, C. J., Parulekar, W. R., Summerskill, W. S., Groves, T., Schulz, K. F., Sox, H. C., Rockhold, F. W., Rennie, D. and Moher, D., "SPIRIT 2013 statement: defining standard protocol items for clinical trials," Ann Intern Med 158(3), 200-207 (2013).
- [2] Schulz, K. F., Altman, D. G., Moher, D. and Group, C., "CONSORT 2010 Statement: updated guidelines for reporting parallel group randomized trials," Open medicine : a peer-reviewed, independent, open-access journal 4(1), e60-68 (2010).

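### Two primary ICDAS outcomes at two visits have no order or alpha rule, and the Data Analysis section names no single confirmatory contrast or model

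*Combined protocol and SAP*

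**What the plan says.** All the relevant text is in the Synopsis.

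- **Primary study outcome measures** lists two items: "Differences in change in ICDAS scores between matched case and control teeth (within patient) from baseline to 6 months and baseline to 12 months" and "Differences in occurrence of ICDAS 3 scores between matched case and control teeth (within patient) from baseline to 6 months and baseline to 12 months". Neither is ranked above the other, and neither visit is ranked above the other. Under Framework, superiority is ticked and exploratory is not.
- **Hypothesis** is framed over 12 months, but refers the reader onward to the outcome list for detail.
- **Sample size calculation & statistics** speaks of one primary endpoint, change in ICDAS. It powers one McNemar test of worsening at 5%, with 50 pairs, 75% discordant and a difference of 0.35, and gives no visit. It says that the primary analysis will be a proportional-odds mixed model on differences in scores, and also expects extra power from a Wilcoxon signed-rank test.
- **Data Analysis** opens with "The primary analysis of this study will compare ICDAS scores for the laser group vs. controls". It does this through "mixed effects proportional odds regression modeling with outcomes of ICDAS and SOPROLIFE scores", with group as main predictor, tooth site, an open-ended list of moderators, and interactions of those moderators with group and with time. Then: "The models will be explored in a bottom up approach with each predictor considered in models one at a time along with group", each model also carrying a group-by-predictor interaction and tooth site. Next: "If we see important effects, we will then combine a small number of predictors based on scientific plausibility in a single model". The section adds that "these will be far from definitive models given the sample size and scope of the proposed study", and that P at or below "0.05 will be considered statistically significant though we will emphasize that any model results are highly speculative".

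**The concern.** The model family, the comparison and the main predictor are fixed. The test is not. Someone following the plan would obtain a group term from each one-at-a-time model, another from any combined model, and results at two visits. Occurrence of ICDAS 3 is listed as primary but has no stated analysis. One unsplit 0.05 threshold covers everything. In each named moderator model the group term sits beside a group-by-predictor interaction, so its meaning depends on that predictor and on how it is coded.

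At stake is whether a reader of the results could tell which P-value answers the superiority question. If that can be settled after the data are seen, by choosing among outcomes, visits and models, the nominal 5% no longer describes the trial's claim. The power statement, which is for one unsplit test, would not describe it either.

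**Working it through.** **Step 1. Count the contrasts.** Two primary outcomes × two visits = 4. On the narrower reading in the sample size section, where change in ICDAS is the only primary endpoint, the count is 1 × 2 = 2, because no visit is chosen.

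**Step 2. Reproduce the plan's power.** The inputs, all from the sample size section, are n = 50 pairs, discordant proportion 0.75, difference 0.35 and alpha 0.05. Sidedness is not stated; two-sided is assumed because it reproduces the stated figure.

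- Discordant cells: (0.75 + 0.35)/2 = 0.55 and (0.75 − 0.35)/2 = 0.20.
- The number of discordant pairs M follows Binomial(50, 0.75). Given M, the number favouring laser follows Binomial(M, 0.55/0.75).
- Power is the sum, over M, of the probability that the two-sided exact binomial test of 0.5 rejects.
- Result: 79.8%, which matches the stated 80%.

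**Step 3. Power if alpha is split equally.** The calculation is the same with a smaller alpha.

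| Contrasts sharing 5% | Alpha each | Power, 50 pairs | Independent pairs for about 80% |
|---|---|---|---|
| 1 | 0.05 | 79.8% | 51 |
| 2 | 0.025 | 71.3% | 60 |
| 4 | 0.0125 | 60.8% | 70 (80.1%) |

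This applies the discordance and difference given for worsening to every contrast. The plan gives no such figures for ICDAS 3.

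**Step 4. Chance of at least one rejection under no effect, with each contrast tested at two-sided 5%.** The documents give no correlation between contrasts, so I assume standard normal test statistics with a common correlation ρ. With φ and Φ the standard normal density and distribution function, and c = 1.96, for k contrasts:

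- Any rejection = 1 − ∫ φ(g) [Φ((c − √ρ g)/√(1−ρ)) − Φ((−c − √ρ g)/√(1−ρ))]^k dg.
- False claim of laser benefit = the same, without the lower-tail term.

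| Assumed ρ | Any rejection, k = 2 | Any rejection, k = 4 | False benefit, k = 2 | False benefit, k = 4 |
|---|---|---|---|---|
| 0.9 | 7.0% | 9.4% | 3.5% | 4.7% |
| 0.7 | 8.3% | 13.0% | 4.2% | 6.5% |
| 0.5 | 9.1% | 15.6% | 4.5% | 7.8% |
| 0.3 | 9.5% | 17.4% | 4.8% | 8.7% |

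For one test the figures are 5% and 2.5%. In a superiority trial the false-benefit columns matter more, because a rejection in favour of control is not a claim for the laser.

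**Step 5. Limit on the four-contrast figures.** All study teeth start at ICDAS 0 to 2, so transitions to 3 may be few, and an exact paired test is then conservative. With 50 pairs and a nominal 5%, the exact McNemar test rejects 0.9% of the time under the null if 10% of pairs are discordant, and 2.2% if 20% are (assumed values). The k = 4 columns are therefore an upper guide. In the other direction, none of these figures counts the further choice among the one-at-a-time and combined models.

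**The case against.** The best defence is that the primary question is already clear. The Data Analysis section opens with laser versus control on ICDAS, the sample size section names change in ICDAS as the primary endpoint and gives the model family, and the hypothesis points to 12 months. On this view the stepwise text concerns moderators only. The plan is a phase II trial that is candid about calling its model results speculative and in need of independent verification.

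Part of this stands. Reading only the moderator work as exploratory is reasonable, and the candour lowers the severity. But even on that reading no visit, contrast or interaction-free model is named, the status of ICDAS 3 is unresolved, and the hypothesis refers back to the outcome list with its two visits. The speculative label is attached to any model result, and no other model is offered for the primary comparison.

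A reader might infer more than the documents support:

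- *That the trial's error rate is 17%.* The plan states no rule that any significant contrast counts as success. The figure is two-sided, needs the lowest assumed correlation, and is an upper guide.
- *That individual tests exceed 5%, or that the 80% power is wrong.* Neither follows. The power reproduces for the stand-in test.
- *That power would fall to 60.8%.* That is a worst case: an equal four-way split, 50 pairs and the reduced difference. At the pilot difference of 0.56, power at alpha 0.0125 is 99.4%. The plan also expects to enrol 70 to 80 subjects, some with more than one pair, although pairs from one patient are not independent.
- *That the group coefficient will be misread, or that repeated scoring of a tooth will be ignored.* The plan states neither a coding nor a random-effects structure beyond accounting for clustering within patient. These are points to specify, not errors shown.

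**Conclusion.** The concern holds, and should be fixed before the data are analysed. The plan claims superiority but leaves open which of four primary contrasts, and which model, gives the answer, while its power covers one test. The wording about non-definitive and speculative models softens this without identifying the confirmatory test.

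If the open choice were exercised freely, the chance of a false claim of benefit would rise from 2.5% to 3.5–4.8% on the two-contrast reading, and to at most about 4.7–8.7% on the four-contrast reading. The corresponding two-sided rates are 7.0–9.5% and 9.4–17.4%, against 5%. These rest on assumed equal correlations of 0.9 to 0.3 and normal test statistics, and the McNemar figures are a stand-in for an ordinal mixed model. The gap in the text does not depend on any of these assumptions.

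**What to change.** In the Data Analysis section:

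1. Name one primary proportional-odds mixed model with group, visit, group-by-visit and tooth site, no group-by-moderator interactions, and random effects that cover both the patient and repeated scoring of the same tooth. State a fallback in case it cannot be estimated.
2. Name one primary contrast. Laser versus control on ICDAS at 12 months fits the hypothesis and the sample size section. State whether it is on change or on baseline-adjusted score; these differ in a proportional-odds model, and the outcome list, sample size and analysis sections must agree.
3. Make the other three contrasts secondary, or test them in a stated fixed order.
4. Give occurrence of ICDAS 3 its own paired analysis. Any McNemar or Wilcoxon analysis, including a fallback, must handle patients with more than one molar pair, for example by one summary per patient or a cluster-adjusted version. State the role of the Wilcoxon test mentioned in the sample size section.
5. State how participants whose study endpoint is reached at 6 months, as described under Clinical Study, enter the 12-month contrast.
6. Move the one-at-a-time and combined models to a section labelled exploratory, which cannot alter the primary result.

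The cost is text only, with no extra patients or visits, and all moderator work is kept. The sponsor must commit to one contrast or an order. Either choice keeps 79.8% stand-in power for the first test. An equal split over all four would lower it to 60.8% at 50 pairs, or need about 70 independent pairs to restore 80%.
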